- a. **Recruitment Sites:** To maximize recruitment, while WIC is conducting visits virtually, data queries and phone screening by WIC staff will include participants from all 10 of Philadelphia WIC's community clinic sites. Once sites resume in-person visits, we will resume in-person recruiting.
 - i. North Philadelphia WIC Clinic, [name]
 - ii. Olney-Logan WIC Clinic, [name]
 - iii. Aramingo WIC Clinic, [name]

- iv. South Philadelphia WIC Clinic, [name].
- v. Northeast WIC Office, [name].
- vi. Overbrook WIC Office, [name]
- vii. Woodland WIC Office, [name].
- viii. St. Christopher WIC, [name]
- ix. Lehigh WIC Office, [name]

b. Research Procedures Site:

Assessment visits (combined CORE Screening/Enrollment (CS/EN) [\leq 16 weeks gestation], end of pregnancy [36-38 weeks' gestation], 6-months postpartum, and 12-months postpartum) will occur over the phone with Temple research staff member. All staff will complete calls from a private space.

If public health guidelines allow and participants consent, these calls may be conducted as in-person visits at Temple's CORE office ([name]) or if transportation is an issue, we will conduct these visits at the participants' home.

7) Prior Approvals

WIC is strongly supportive of our efforts (see updated approval letter attached from WIC).

8) Study Design

a. Recruitment Methods: Up to 600 women will be recruited and consented for this study. We plan to enroll and randomize a total of 438 participants (219 per arm). Based on prior studies ([name] PI, Protocol #20227, "The effects of an electronically-mediated, pregnancy and postpartum, behavioral intervention program on changes in weight and cardiometabolic biomarkers: Healthy4Baby" NIH K23HL106231-01 and [name] PI, Protocol #22201, "Targeting pregnancy-related weight gain to reduce disparities in obesity: a randomized control trial" HRSA R40MC26818), we will likely need to recruit and screen approximately 40% more women than our randomization target (as we anticipate no-shows to baseline visits).

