- i. **Primary outcome.** *The primary outcome is the proportion of women with excessive gestational weight gain*, defined as the proportion of mothers exceeding weekly Institute of Medicine (IOM) weight gain targets (>0.32 kg/week for BMI 25-29.9 kg/m²; >0.27 kg/week for BMI ≥ 30 kg/m²) over the study period (from enrollment to end of pregnancy).⁵⁷ Total gestational weight gain will be calculated as the difference between weight in kilograms measured at 36-38 weeks' gestation (end of pregnancy) and weight at the baseline visit (in the first trimester or early second trimester of pregnancy). Weight in clinical gowns, without shoes, will be recorded in duplicate by trained staff using high-quality, calibrated SECA digital scales. We will also use BodyTrace scales for patients seeking a remote option (and/or during restrictions to in-person visits during the Covid-19 pandemic) that will be sent to the participant after completion of the combined CS/EN call. In the rare case that a mother delivers her infant before 36-38 weeks' gestation, we will abstract her last prenatal weight from her obstetric chart and call her within 2 weeks of delivery to administer our follow-up

survey. We expect to abstract weights in <10% of mothers based on previous experiences with the target population. Height will be measured to the nearest 0.1 cm using a calibrated stadiometer at participants' in-person baseline assessments or via self-report via phone.

ii. **Secondary and patient-centered outcomes.**

1. ***Dietary intake*** will be measured using the Automated Self-Administered 24-hour (ASA24) dietary assessment tool, a web application developed by NCI.⁶⁹ We will collect one 24-hour dietary recall during combined CS/EN visit or call and during the end of pregnancy visit. Data are summarized as intake of micro- and macronutrients, food groups, and dietary patterns. ASA24 has been validated against more expensive, time-consuming tools.⁷¹ We have experience using this measure in diverse groups.^{48,49}

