4. **Power and sample size.** Sample size estimates were determined to ensure power for detecting differences in trial arms on the primary study outcome, the proportion of women with excessive gestational weight gain. We used results from

our own preliminary studies along with published data from earlier trials in obese pregnant women to approximate our ability to detect differences in weight gain between trial arms. In our pilot study, Healthy Babies, 37% of intervention participants gained in excess of IOM guidelines compared to 66% of usual care.¹⁹ We recognize, however, that our pilot study's sample size was small, and thus, ***we have made a more conservative assumption for the power analysis in this proposal*** – 15% difference between healthy lifestyle intervention and usual WIC care arms (e.g., prevalence of 40% in the intervention arm vs. 55% in usual care) – based on data that includes a range of between-group differences, from 12% to 30%.^{15,49} Sample sizes of 186 per arm will provide power of at least 0.8 with a 2-sided alpha of 0.05. If the difference is 20% (e.g., 40% vs. 60%), the power will be at least 0.96. Conservatively assuming we will lose 15% for miscarriage or loss to follow-up, the required sample size is 219 subjects per arm or 438 total.

10) Withdrawal of Subjects

Participation in this study is completely voluntary. Participants may refuse to participate or stop participation in this study at any time and it will not affect their present or future care at WIC or Temple University.

11) Privacy & Confidentiality

Information about study subjects will be kept confidential and managed according to the requirements of the Health Insurance Portability and Accountability Act of 1996 (HIPAA). Those regulations require a signed subject authorization informing the subject of the following:

- What protected health information (PHI) will be collected from subjects in this study
- Who will have access to that information and why
- Who will use or disclose that information
- The rights of a research subject to revoke their authorization for use of their PHI.

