Risks to subjects are minimal and therefore reasonable in relation to the anticipated benefits to the research subjects and society as a whole.

14) Costs to Subjects

If participants agree to take part in this research, they will receive \$100 after completing all CS/EN questionnaires and being officially enrolled (to reimburse participants for time and travel). All enrolled participants will also receive a diaper bag and a scale to weigh themselves at each study time point after their CS/EN call. Mothers in the intervention group will have a water bottle, measuring bowls & spoons, and a cookbook included in their bag. Enrolled participants will additionally receive \$75 after completion of their 36-week gestation call, and \$50 after completion of their 6-month and 12-month postpartum calls. Total compensation for completing all assessments will be \$275.00 (for both groups). Participants will either be texted or emailed VISA e-gift cards (preferred method) or mailed plastic VISA gift cards at the end of each visit. Participants in the intervention group will also be eligible to win a monthly raffle prize, valued between \$75.00 and \$100.00. Intervention participants will receive 1 raffle entry for each monitoring text they send. Monthly raffles will be held (run by study staff) on the last day of every month and winners will be contacted via text message. Septa passes will also be provided for transportation (if needed).

15) Informed Consent

All subjects for this study will be sent a consent form via e-mail or mail prior to the combined CS/EN call or visit. During the initial call/visit, study staff will review the Informed Consent describing this study and providing sufficient

information for subjects to make an informed decision about their participation in this study. The consent form is submitted with this protocol for review and approval by the IRB. The formal consent of a subject, using the IRB-approved consent form must be obtained before that subject is submitted to any study procedure.

Consent will be obtained electronically via Redcap prior to any study procedures being completed. Study staff will be trained to consent patients and provide a detailed explanation of all procedures, risks, and benefits.

Additionally, participants will be sent or given paper copies of their signed Informed Consent Form, the HIPAA Authorization, and the Medical Record Release forms (prenatal, delivery, infant, and WIC)

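### The two weights behind the primary endpoint may come from different sources in the same woman, with no same-source rule, no home-weighing conditions and no sensitivity analysis by source

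*Combined protocol and SAP*

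**What the plan says.** **Endpoint (section 9.d.i).** A woman is a case if her weekly gain from enrolment to the end of pregnancy exceeds 0.32 kg/week (BMI 25-29.9) or 0.27 kg/week (BMI 30 or more). The gain is the 36-38 week weight minus the baseline weight.

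**Two main sources.** In person, "Weight in clinical gowns, without shoes, will be recorded in duplicate by trained staff" on calibrated SECA scales. The same paragraph then says: "We will also use BodyTrace scales for patients seeking a remote option". It states no clothing, shoe or repeat rule for the home reading.

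**Choice of source.** Section 9.b (Weight and height) permits either source at each time point. Section 6.b makes telephone assessment the norm, but adds: "If public health guidelines allow and participants consent, these calls may be conducted as in-person visits".

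**Scale supply.** Section 8.c.viii sends phone-enrolled women a BodyTrace scale for all time points. Section 9.b sends it after the enrolment call or visit. Section 14 says: "All enrolled participants will also receive a diaper bag and a scale to weigh themselves at each study time point".

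**Analysis (section 9.d.iii.1).** The plan asserts high agreement between research weights and prenatal clinic weights. It says nothing about SECA against BodyTrace, and nothing about source in the primary analysis.

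**The concern.** A constant difference between two weighing methods cancels in a change score only if the same method is used at both ends. For a woman weighed in a gown on SECA at baseline and on BodyTrace at home at 36-38 weeks, the difference between methods enters her gain in full. With the reverse sequence it enters with the opposite sign. The gain is then dichotomised, so a woman near her cut-off can change class.

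The sequence follows from the text. Because section 9.b sends the scale after the enrolment visit, a woman enrolled in person has no BodyTrace reading from that session. If her late-pregnancy assessment is by phone, as section 6.b expects, her gain is BodyTrace minus SECA.

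The mode at 36-38 weeks is also settled after randomisation, and only intervention women are prompted to weigh themselves weekly at home (section 9.c.iii, self-monitoring texts). It is therefore possible, though not shown, that the source mix differs by arm. If it did, the treatment comparison would be biased as well as noisier.

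**Working it through.** **1. The plan's sample size reproduces.** Inputs from section 9.d.iii.4: "prevalence of 40% in the intervention arm vs. 55% in usual care"; "Sample sizes of 186 per arm will provide power of at least 0.8 with a 2-sided alpha of 0.05"; "Conservatively assuming we will lose 15% for miscarriage or loss to follow-up".

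- Uncorrected: n0 = [1.96·√(2·0.475·0.525) + 0.8416·√(0.40·0.60 + 0.55·0.45)]² / 0.15² = 172.8.
- Continuity-corrected: n = (n0/4)·[1 + √(1 + 4/(n0·0.15))]² = 185.9, so 186 per arm.
- Loss: 186/0.85 = 218.8, so 219 per arm and 438 in total.
- Power at 186 per arm is 0.800 corrected and 0.811 for exact Fisher. For the second scenario ("If the difference is 20% (e.g., 40% vs. 60%), the power will be at least 0.96") the corrected value is 0.966.

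These figures are sound, and nothing below changes them.

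**2. From offset to weekly rate.** Entry is by 16 weeks, so the interval is at least 36 − 16 = 20 weeks, and longer with earlier entry. Rate error = offset / weeks.

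| Offset (assumed) | Over 20 weeks | Share of 0.27 | Share of 0.32 |
|---|---|---|---|
| 0.5 kg | 0.025 kg/week | 9% | 8% |
| 1.0 kg | 0.050 kg/week | 19% | 16% |
| 2.0 kg | 0.100 kg/week | 37% | 31% |

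The total gain at the cut-off is 20 × 0.27 = 5.4 kg to 26 × 0.27 = 7.0 kg for BMI 30 or more, and 6.4 to 8.3 kg for BMI 25-29.9. Only women whose true gain lies within the offset of that total can change class.

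**3. Share reclassified.** The documents give no SD of weekly gain. I assume a normal distribution with SD 0.15-0.30 kg/week, placed so that a proportion p exceeds the cut-off. An upward offset changes p to Φ(Φ⁻¹(p) + offset/(weeks·SD)).

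Example with 1 kg, 22 weeks and SD 0.20: the shift is 1/(22 × 0.20) = 0.227 SD. For p = 0.55, Φ(0.126 + 0.227) = 0.638, a rise of 8.8 points. For p = 0.40, Φ(−0.253 + 0.227) = 0.490, a rise of 9.0 points.

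Over 20-24 weeks and the full SD range, the share of mixed-source women who change class is:

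- 0.5 kg: about 3-7%
- 1 kg: about 5-13%
- 2 kg: about 10-26%

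**4. Balanced arms.** Take the extreme case in which every woman is mixed-source, 186 per arm, continuity-corrected:

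- 1 kg, all in one direction: power 0.79-0.80
- 1 kg, half up and half down: power 0.75-0.79
- 2 kg, half up and half down: power 0.60-0.77

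With fewer mixed women the loss is smaller.

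**5. Mix differing by arm.** Take no true effect (55% in both arms), 22 weeks, and a 20-point difference between arms in the share of mixed women, all mixed in the same direction. Spurious difference = 0.20 × the reclassified share. The standard error is √(2·0.55·0.45/186) = 0.0516.

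| Offset | Spurious difference | Two-sided type I error |
|---|---|---|
| 0.9 kg | 1.1-2.1 points | 0.055-0.069 |
| 2.0 kg | 2.3-4.4 points | 0.073-0.135 |

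For 1 kg the reclassified share at p = 0.55 is 5.9-11.6%, so the spurious difference is 0.20 × that, or 1.2-2.3 points.

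**The case against.** The strongest reply is that mixed pairs are not the planned route. Assessments are by phone unless circumstances and the woman allow otherwise, phone enrolees get a BodyTrace scale for every time point, and all enrolled women receive one. BodyTrace at both ends should therefore be common, and such a pair has no between-instrument offset. This stands: the number of mixed-source women is unknown and may be small.

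The clothing difference is inferred, because the plan is silent on clothing at home. The offset, the SD and the 20-point imbalance are also assumptions. This stands too, and is why only ranges are given.

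The direction may be harmless. If home readings run heavier and intervention women are the ones more often on BodyTrace at 36-38 weeks, their measured gain rises relative to usual care and the benefit is understated. That is fair for this particular mechanism. But the documents establish neither the sign of the offset nor which arm would be more mixed, and both arms receive a scale and the same assessment payments.

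Two further inferences should be resisted. A reader might take section 6.a to mean that outcome weighing will switch back to in-person as sites reopen, but that passage concerns WIC visits and recruiting. A reader might also see a conflict over who receives a scale between sections 8.c.viii and 14. Section 9.b already covers supply after a call or a visit, so no alignment is needed.

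None of this supplies a same-source rule, home-weighing conditions or an analysis by source.

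**Conclusion.** The gap is real and its likely effect is modest. As written, a woman enrolled in person and followed by phone contributes a cross-instrument gain to the primary endpoint, and the plan has no means of preventing, identifying or testing this.

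Under the assumed 1 kg, 20-24 weeks and SD 0.15-0.30 kg/week, about 5-13% of mixed-source women change class. With a balanced mix, the consequence is a shifted prevalence and a small loss of power, not a false positive. With a 20-point imbalance between arms, the contrast moves by about 1-2 points, against the 15 points planned.

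A reader might infer that the offset would carry a typical woman across her cut-off, or that the trial's comparison is already biased. The documents support neither: only women near the cut-off are affected, no offset is given, and nothing shows that the mix will differ by arm. The sample size is not in error.

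**What to change.** Add to section 9.d.i:

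- **Same source at both ends** wherever both are available. Use SECA to SECA when both visits are in person.
- **In-person enrolment:** have the woman's scale at the visit, and take a BodyTrace reading in the same session, before randomisation, alongside the SECA weight. These pairs also give the trial its own estimate of the offset.
- **In-person 36-38 week visit for a woman with a BodyTrace baseline:** also obtain a BodyTrace reading within the window.
- **Home weighing:** the same instructions in both arms on clothing, no shoes and duplicate readings.
- **Recording and analysis:** a source field at each end, source pairs reported by arm, and a sensitivity analysis limited to same-source pairs or adjusted for source pair. This should stay a sensitivity analysis, because the follow-up source is determined after randomisation.

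Do not make BodyTrace the default baseline for phone enrolees on this ground. Their scale is sent after the call that includes randomisation, so that reading would follow randomisation. Which baseline weight those women contribute is a separate issue.

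The cost is protocol wording, one extra reading on a scale already supplied and one data field. For women already enrolled, the reporting and sensitivity analysis remain possible wherever the source can be recovered. The sample size stays at 219 per arm.

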
2) Protocol Title

Partnering with WIC to prevent excessive weight gain in pregnancy

3) Investigator

[name], MPH

4) Objectives

a. Primary specific aim: To determine whether the healthy lifestyle program lowers the prevalence of excessive gestational weight gain, compared to usual WIC care. Primary hypothesis: Participants randomized to the healthy lifestyle intervention arm will demonstrate significantly lower prevalence of excessive gestational weight gain, compared to those randomized to usual WIC care.

b. Additional aims:

- i. To compare trial arms with respect to changes in diet and physical activity, and rates of adverse pregnancy outcomes (including glucose intolerance, hypertension, and infant macrosomia).
- ii. To utilize the RE-AIM framework to evaluate the intervention's dissemination potential in WIC. We will assess: reach into the patient population; effectiveness on outcomes; organizational adoption; consistency of implementation; and maintenance of effects on 6- and 12-month maternal/child postpartum weights.
- iii. To quantify the intervention's cost-effectiveness.

5) Rationale and Significance

Nearly two-thirds of pregnant women exceed Institute of Medicine (IOM) weight gain guidelines.¹ Excessive gestational weight gain not only adversely affects the current pregnancy – by increasing risk of diabetes and hypertension, cesarean delivery, and infant macrosomia – but it also promotes new or persistent obesity in women and their children.^{2,3} Ethnic minority women are at particular risk of greater gains because they are more likely to enter pregnancy obese,⁴ reside in obesogenic environments,⁵ and adopt obesity promoting behaviors (e.g., high caloric intake, physical inactivity).⁶⁻⁸ However, these high risk women also suffer from a paucity of treatments. Without intervention, the implications are clear: most will exceed recommended gains in pregnancy and incur significant morbidity for themselves and their children.^{9,10}

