b. Recruitment via advertisements and flyers: Study advertisements will be used and are attached. Subjects will be deemed eligible for screening by completing a phone screen with a WIC staff member. The phone screen will include questions related to determining if the subject meets the study's initial inclusion and exclusion criteria (see section 8e below for inclusion/exclusion

criteria). Research staff will devote time daily to fielding phone calls, scheduling study subjects for screening visits, and conducting screening visits.

c. **Recruitment via WIC's electronic patient database:** Potential participants for this clinical trial will include patients identified through WIC's electronic patient database, using the eligibility criteria described in the inclusion/exclusion criteria section below. We will target patients who are seen at the WIC sites described in the recruitment site section above (6a). [name], WIC Executive Director, has provided an updated letter of support for this study and its recruitment approach (see approval letter attached to this protocol). We've used a similar approach in previous studies. We are requesting a HIPAA waiver in order to identify potentially eligible patients via WIC's electronic patient database.

- i. Criteria used to develop the computable phenotype:
 1. Age in years (≥ 18 years)
 2. Currently pregnant (≤ 16 weeks' gestation) within 30 days of the data query
 3. $BMI \geq 25\text{kg/m}^2$ within 30 days of the data query
- ii. Once a list of patients is generated using this phenotype by WIC staff, an IRB-trained WIC staff member [name], [name], or [name] will text message or call identified patients in English and/or Spanish and explain the purpose of the study, assess interest, and evaluate eligibility (see WICProvider/Phone screen for script and eligibility questionnaire). All Spanish speaking participants will be screened by [name], who is bilingual. Participants who are initially eligible after phone screening (see inclusion/exclusion criteria below) will be scheduled for a combined CS/EN call or visit where they will be immediately consented in English or Spanish for the study by Temple study staff (note, all study visits for Spanish speaking participants will be administered by [name], who is bilingual).

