4. ***WIC provider counseling:*** There is evidence that WIC counseling is trusted,⁵⁴⁻⁵⁶ yet WIC nutritionists find it difficult to adequately address gestational weight gain at routine visits.²⁷ Our treatment is designed to encourage a patient-centered counseling approach (e.g., responsive to individual preference, needs, and values) while at the same time overcome barriers, including: time constraints (by supplying progress reports and brief recommendations); failure to follow-up in-between visits (which will be largely automated); and fear of causing offense (which will be resolved through role play and group discussion). There is strong support for integrating our intervention into WIC care (see letter from initial IRB submission). Participants will have monthly to bimonthly study-related phone calls from a WIC nutritionist (aka, WIC Champion, [name]) to set goals, overcome challenges, and give participants new information about diet and activity while they are in the program. These calls will last 15- 30 minutes and will be audiotaped (for training and feedback). Additionally, if participants agree, they will also receive in-person support at their regularly scheduled WIC visits every 2-3 months. While WIC is conducting visits virtually, we will not be using this approach. To inform counseling, we will supply the WIC champion with coaching protocols for new goal assignment calls that will be adapted from our prior pregnancy and postpartum weight control trials during study start-up. The goal assignment calls will take place in 8 week intervals for each participant. Additionally, the WIC champion will be notified when a participant in this group is -0.3kg from her weekly maximum IOM recommended weight gain targets or above⁵⁷ and the WIC champion will be asked to call these participants within 48 hours using adapted problem solving call scripts to enhance motivation for behavior change, deliver in-depth skills training, engage in problem solving, and provide social support. We will set a call ceiling of 1, 15-30 minute call monthly so to not overburden providers, but instead harness a potentially

important opportunity for impacting behavior change and ensuring safety.

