Effectiveness will be assessed via our primary, secondary and patient-centered outcomes.

Adoption is a measure of potential intervention uptake by WIC. We will quantitatively assess number of provider referrals for study entry.

Implementation will be examined on both the participant level and the WIC provider level. At the participant level, we will measure intervention engagement via: 1) number of responses to self-monitoring text prompts, text response time, and the type/frequency of texted videos viewed; 2) type/frequency of FB or Instagram posts and/or likes; and 3) number/duration of WIC provider visits and calls completed. Relying on an approach by Olson and colleagues, we will examine the extent to which level of engagement is associated with gestational weight gain.⁸⁵ We will also evaluate the consistency of the intervention across different patient/provider subgroups. At the WIC provider level, we will examine process data stored in our web application and perform chart reviews to assess documentation of weight-related counseling to measure intervention delivery fidelity.

Maintenance of weight change will be assessed at 6- and 12-months postpartum. We will determine the proportion of women in each treatment group at (+/- 0.9kg) or below early pregnancy weight by 6 months and 12 months postpartum. While observational data repeatedly suggest that excessive gestational weight gain is the strongest predictor of postpartum adiposity,³ few studies have evaluated this relationship in the context of a clinical trial. With participant consent, we will additionally abstract their infant's weight and length from their pediatrician visits. These will be used to approximate measures at 6-months and 12-months of age and assess maintenance of intervention effects on infant weight/length.

iii. **Data analysis plan:**

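### Organisational adoption rests on one count of provider referrals into the trial, with no denominator and no described referral step, so it is a poor measure of whether WIC takes the programme up

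*Combined protocol and SAP*

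**What the plan says.** Section 4(b)(ii) sets the aim of judging dissemination potential in WIC: "We will assess: reach into the patient population; effectiveness on outcomes; organizational adoption; consistency of implementation". Section 9(d)(ii)5 then gives the meaning and the measure of adoption in two sentences: "Adoption is a measure of potential intervention uptake by WIC", followed by "We will quantitatively assess number of provider referrals for study entry". Nothing else appears under Adoption.

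Recruitment is described in three places.

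- **Section 8(b), advertisements and flyers:** "Study advertisements will be used and are attached". Women who respond are phone-screened by WIC staff.
- **Section 8(c), database:** "Potential participants for this clinical trial will include patients identified through WIC's electronic patient database". The next step is "Once a list of patients is generated using this phenotype by WIC staff, an IRB-trained WIC staff member" (one of three named individuals) texting or calling the women listed. The list is refreshed every 30 days.
- **Section 6(a), in person:** recruiting at clinics restarts when clinics see patients again.

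On delivery, Section 9(c)(iii)4 assigns the study phone calls to a WIC Champion and adds optional in-person support at routine WIC visits. Of that support it says: "While WIC is conducting visits virtually, we will not be using this approach". Under Implementation, Section 9(d)(ii)5 plans provider-level process data from the web application, and chart review of weight-related counselling. Section 9(d)(iii)2 makes all RE-AIM analyses exploratory.

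**The concern.** The construct and the measure do not match. Adoption is meant to show whether WIC, as an organisation, would take the programme up. The measure counts something that happens before randomisation and does not require anyone at WIC to use any part of the programme. A nutritionist could refer many women and never open a progress report. Another could use the reports routinely and refer nobody, because the database query had already found her patients.

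This bears on the reason for the trial. Section 5 says the pilot's dependence on research staff limited its dissemination potential, and argues that the approach could be scaled across WIC. Whether ordinary clinics and nutritionists use the programme is the open question, and it is the one that an adoption result will be read as answering.

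**Working it through.** The plan gives no figure for adoption, so this is mainly a comparison of its own sections.

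**1. Does the measure match the definition?** The definition concerns uptake of the intervention. The measure concerns entry to the study. Under Section 8(c)(vii), women who enter are randomised 1:1, 219 to each arm, so 219/438 = 50% receive usual WIC care. On average, half of the referred women who are randomised never receive the programme.

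**2. Can the described routes produce a provider referral?** There are two readings of the term.

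- *A nutritionist sends a patient to the study.* No such step appears in Section 8(b) or 8(c), and Section 6(a) gives no provider role for in-person recruiting. Referrals could still occur informally, but the plan neither describes nor defines them.
- *The WIC screener passes a willing woman to the research team* (Section 8(c)). This step exists. The count then largely repeats Reach, which already covers the proportions of eligible women who are reached, interested and enrolled.

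Neither reading measures uptake.

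**3. Can the count become an uptake proportion?** It has no denominator. Take Section 6(a)'s statement of 10 clinics. Any total of at least 10 referrals is compatible with one referring clinic (1/10 = 10%) or with all ten (10/10 = 100%). The total does not separate these cases.

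**4. Is the clinic denominator settled?** Section 6(a) states 10 sites, but the list runs from i to ix, which is nine. The public text may have lost an entry. One clinic is worth 1/10 = 10.0 percentage points or 1/9 = 11.1, so the number needs confirming before it is used.

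**5. Do better data exist in the plan?** Yes, under other headings. Section 9(d)(ii)5 plans web-application process data and chart review, both labelled delivery fidelity. Section 9(b) plans extraction of the nutrition topics discussed at WIC visits. Section 5 names the components given to providers: electronic progress reports and counselling recommendations. Use of these is much closer to the plan's own definition of adoption.

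**6. Would any weight-related counselling count?** No. Under Section 9(c)(ii), WIC providers have self-help materials and quarterly obesity-treatment trainings as part of usual care, and Section 9(c)(iii) adds the intervention to that. Charted counselling alone cannot be credited to the programme.

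**The case against.** The best defence is that adoption is defined as potential uptake, and a provider's willingness to refer is some sign of potential. The outcome is exploratory, no arm comparison depends on it, and much of the relevant provider-level data is already planned under Implementation. On this view the point is mostly about which RE-AIM heading holds which data.

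Much of that stands, and it rules out several stronger readings.

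- A reader might infer that the count must come out near zero. The documents give no referral data. The database wording is not exclusive, the advertisements and screening script cannot be seen, and in-person recruiting may resume. An undescribed route is not an absent one.
- A reader might infer that enrolment runs only through the database. Advertisements and later in-person recruiting are also planned.
- A reader might say that the count carries no information. That is too absolute, since referrals could weakly reflect provider goodwill.
- A reader might conclude that one person delivers all the counselling calls. Section 16 assigns Champion calls for Spanish speakers to bilingual staff, so a single deliverer is not established.

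The mismatch itself remains. Exploratory status does not make a recruitment count informative about uptake. Leaving the better data under Implementation means that the result reported as adoption will still be the referral count.

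**Conclusion.** The point holds as a measurement weakness in one exploratory outcome. As written, the plan cannot give a usable answer to the organisational-adoption part of aim 4(b)(ii), because the only measure reflects recruitment, has no denominator, and has no described pathway that would produce it. The size of the distortion cannot be put as a number from the documents. The primary outcome, alpha, power and sample size are not affected.

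The conclusion assumes that Sections 6(a), 8(b) and 8(c) describe the main recruitment routes. If an attached script or flyer contains a formal referral step by nutritionists, the pathway objection falls. The mismatch between referral and uptake, and the missing denominator, would remain.

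**What to change.** - **Move referrals.** Report provider referrals under Reach as a recruitment source, with a definition of what counts as one.
- **Redefine adoption.** Use the share of participating WIC clinics with documented use of intervention components, such as progress reports or counselling recommendations, for women in the intervention arm. Give the share of nutritionists as well where records identify them. Take both from the planned web-application data and chart review. With about ten clinics, report this descriptively as a count out of the total.
- **Exclude non-specific activity.** Do not count general weight-related counselling alone. Attendance at the quarterly trainings is not a substitute, because those belong to usual care and the plan does not say that attendance is recorded.
- **Fix the denominator.** Confirm whether there are nine or 10 clinics.
- **Separate the Champion calls.** Report them as delivery by designated study counsellors, not as uptake by routine WIC providers.

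The cost is a change of protocol wording, some re-tabulation and, if the chart form does not already capture component use, one added item. The documents do not say whether the web application logs use by clinic or by individual, so that needs checking first. The adoption figure will probably be lower while visits are virtual, and the report should say why.
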